The proposed study is a 28-week randomized, placebo-controlled, double-blind trial comparing the efficacy of ACTH versus placebo for the treatment of fatigue in patients with RMS (RMS). Ninety patients with RMS who meet all of the eligibility criteria will be enrolled from five participating sites. Eligible patients will be consented by site investigators or delegated research personnel before undergoing any study procedures. Subjects will be randomized to ACTH or placebo at 1:1 ratio.

Endpoints

The primary objective of this study is to assess the efficacy of ACTH versus placebo in reducing fatigability in patients with relapsing MS. The primary endpoint is a statistically significant reduction of fatigue measured by MFIS and FSS, which will be administered at baseline, week 8, 16, 24, and 28.

Secondary objectives include assessment of the tolerability and safety of weekly ACTH treatment vs. placebo and evaluation of ACTH on depression, sleepiness, and quality of life measures and the correlations between measures. The secondary endpoints are measured by BDI-II, ESS, SF-36 at baseline, week 8, 16, 24, and 28. Clinical and laboratory adverse events (AE) and serious adverse events (SAE) will be monitored continuously during the study period to capture safety and tolerability information.

Patient Recruitment

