1. Patient has a relapse during the study. A relapse is defined as a new symptom, or worsening of pre-existing neurologic symptoms, of at least 24 hours duration, in patients who had been clinically stable for the prior 30 days, in the absence of fever, sleep deprivation or severe emotional stress.
2. Patient has an adverse event that presents unacceptable risk judged by the investigator
3. Patient has inadequate adherence to the protocol
4. Patient is lost to follow-up
5. Patient becomes pregnant

Treatment Overview**Dosage and Administration of Acthar® or matching placebo**

The study drug (ACTH 40 units or identical-appearing placebo) will be given subcutaneously twice weekly for 2 weeks. If the patient tolerates this dosage regimen, the dose will be increased to 80 units or placebo twice weekly. If the 80 unit dosage is not tolerated, the dosage will be reduced to 40 units twice weekly for the remainder of the 24 week participation. The weekly doses will be given 3 days apart, for example, on every Monday and Thursday or every Tuesday and Friday. Patients are not allowed to take doses on consecutive days. If a patient cannot take a dose on a scheduled day, the dose can be taken either a day early, or a day late. Patients that forget to take their scheduled dose will be encouraged to take their dose the following day.

Randomization/Treatment assignment and blinding

A total of 90 patients will be randomized either to active drug (ACTH), or placebo in a 1:1 ratio stratified by study site. Each study site will be assigned a site number, and each patient who signed consent form and received a screening test will have a unique study ID, which identifies the patient and the study site at which they participate throughout the study. Within each site, subjects will be randomized in blocks of 4, 2 ACTH and 2 placebo treated patients, to achieve balance in the allocation of subjects to study drug versus placebo arms. The order in which each of the 4 samples is selected will be predetermined by a

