- Physical and neurological exam
- Laboratory assessments: CBC, Urinalysis, CMP
- MFIS, FSS, BDI-II, ESS, SF36, C-SSR*
- Concomitant therapy and AEs

* The C-SSR must be reviewed by the site principal investigator or treating physician prior to the patient leaving the clinic

Unscheduled visits

Patients may be asked to return for unscheduled visit to assess any undesired clinical, or laboratory changes that occur during the study.

Study withdrawal

If a patient is lost to follow-up after all means of contact have been attempted, she/he will be withdrawn from the study.

Patient Monitoring and Evaluation

Patients will be instructed to contact their treating neurologist immediately in the event of a relapse.

A Stage 1 safety and efficacy analysis will be performed when 45th subject has completed visit 4(week 16). This analysis will be performed by the unblinded clinical and biostatistician members of the data safety monitoring board (DSMB). While this analysis is being performed, no new subjects may enroll in the investigation, but treatment of those already enrolled will continue while the analysis is taking place. If more subjects in the placebo arm demonstrate 20% or greater improvement than in the ACTH arm on both the MFIS and FSS, the study will be halted and subjects in the study will cease receiving investigational agents. If the ACTH arm is equal or superior to the placebo arm in MFIS and/or FSS, the study will continue, as will recruitment of the additional 45 subjects. If the study is halted due to lack of efficacy after the Stage 1 analysis, an additional analysis for efficacy will be performed utilizing those subjects who completed 6 months enrollment at the time the study was halted.

Treatment compliance

Patients will be instructed to complete a medication administration log and return the logs to study coordinator at each visit. Information on missed doses and total number of missed doses will be captured. Missing more than 2 doses in an 8-week interval is considered non-compliant. The investigator will discuss the medication regimen with non-compliant patients and they will be encouraged to continue with their injection schedule.

Potential Pitfalls and Contingencies

This study requires self-administration of an injectable agent. Thus there is a risk of non-compliance on the part of the subjects either due to needle phobia, intolerance to injections or lapse memory on the part of the subjects.

Data Processing and Analysis

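### The Stage 1 efficacy rule compares numbers of responders rather than proportions in arms that will often be unequal, and its halt and continue sentences are complementary only under one reading

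*Combined protocol and SAP*

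**What the plan says.** The rule is in section C, Patient Monitoring and Evaluation. The look takes place "when 45th subject has completed visit 4" (Week 16). The halt sentence reads "If more subjects in the placebo arm demonstrate 20% or greater improvement than in the ACTH arm on both the MFIS and FSS", and in that case "the study will be halted and subjects in the study will cease receiving investigational agents". The continue sentence reads "If the ACTH arm is equal or superior to the placebo arm in MFIS and/or FSS, the study will continue".

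Neither sentence gives a denominator, an analysis set or a way to handle dropouts. The plan does not say whether the two-scale condition is met scale by scale or by the same subject on both. It also does not say whether ACTH is judged equal or superior by count, rate or mean change. The DSMB section only refers back to the timing of the interim analysis.

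Other sections bear on arm sizes at the look. Patients "will be enrolled from five participating sites" (Study Design). "Within each site, subjects will be randomized in blocks of 4, 2 ACTH and 2 placebo treated patients" (Randomization/Treatment assignment and blinding). Enrolment is competitive and 20% dropout is assumed (Patient Recruitment). Withdrawn patients are not replaced (Premature termination visit).

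**The concern.** A count is a fair comparison only when the arms are the same size. Here 45 is odd, blocks of four may be open at up to five sites, and withdrawals leave gaps. With the same response rate in each arm, the larger arm tends to have more responders. If placebo is larger, the rule leans towards halting; if ACTH is larger, towards continuing. Neither lean has anything to do with the drug.

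The wording also leaves room for two sentences that do not partition the possible results. Unblinded DSMB members would then have to settle the meaning after seeing data by arm, and the Stage 1 efficacy decision would no longer be prespecified.

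**Working it through.** The plan states no operating characteristic for this rule, so there is no figure of its own to reproduce.

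**1. How unequal the arms can be.** No split of 45 is equal; the closest is 22:23. An open block of four can be out of balance by at most 2. Five sites each out by 2 would make the total leave remainder 2 on division by 4, but 45 leaves remainder 1. The extreme is therefore four sites out by 2 and one out by 1: a difference of 4 × 2 + 1 = 9, or 27:18 among 45 randomised.

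Simulated splits among 45 completers (equal site accrual assumed) give:
- no dropout: arms differ by 3 or more in 31% of trials;
- 20% dropout in each arm: by 3 or more in 55%, by 5 or more in 24%;
- 20% dropout on ACTH and 10% on placebo (assumed): placebo larger by 3 or more in 58%, by 5 or more in 32%.

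**2. Count against rate, without a model.** With 21 ACTH and 24 placebo patients, 7/21 = 8/24 = 33.3%. By count, placebo leads 8 to 7. If this happens on MFIS and on FSS, the rule halts at identical response rates.

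**3. Halt probability, each scale compared separately.**
- From Sample Size Justification: between-group difference 7.6 and SD 16.4, so the effect is 7.6/16.4 = 0.46 SD. A 20% improvement on a baseline of 38 is 0.20 × 38 = 7.6, so the responder threshold is also 7.6/16.4 SD.
- Assumed: normal improvements, the same effect and threshold on FSS, and an MFIS-FSS correlation of 0.6.
- Implied response rates per scale: placebo 1 − Φ(0.46) ≈ 0.32; ACTH under the planned effect 1 − Φ(0) = 0.50.
- P(halt by count) = P(placebo responders > ACTH responders on MFIS, and likewise on FSS). For proportions, each number is divided by that arm's completers.

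| Metric | Planned effect | No effect |
|---|---|---|
| Counts (ACTH v placebo) | 1.5% (23 v 22), 2.9% (22 v 23), 5% (21 v 24), 9% (20 v 25) | 11% (25 v 20) to 46% (20 v 25) |
| Proportions of completers | about 3% at every split | 29-34% |

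With no effect, arm size alone changes the count-based halt probability about fourfold (46/11 ≈ 4.2). At 22 v 23, counts and proportions nearly always agree.

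**4. Averaged over likely splits.** With five sites, blocks of four, competitive enrolment, and assumed site shares and equal dropout, the halt probability under the planned effect, count v completer proportion, is 2.5% v 3.1% (no dropout), 3.0% v 3.1% (10%) and 3.3% v 3.1% (20%). A split of 20:25 or worse for ACTH occurs in about 2%, 8% and 12% of trials respectively.

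**5. Can halt and continue both hold?**
- *Per scale, one responder metric.* Halt requires placebo ahead on MFIS and on FSS. Continue requires ACTH equal or ahead on at least one. Each is exactly the negation of the other, so there is no overlap and no gap.
- *Per subject.* Suppose ACTH has 10 MFIS and 10 FSS responders, 2 of them on both, and placebo has 6 and 6, with 5 on both. Placebo leads 5 to 2 on subjects meeting both (halt), while ACTH leads 10 to 6 on each scale (continue). Assuming no effect, 30% responders per scale and correlation 0.3 to 0.8, at 22:23 or 23:22 both sentences apply in about 16-23% of trials and neither applies in about 2-4%.

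**The case against.** The strongest reply is that this is a matter of wording with little practical effect. Before the arm sizes are known, counts and completer proportions give nearly the same risk of halting an effective drug (step 4). That stands for equal dropout. It does not cover the trial that actually reaches the look with 20 v 25, nor dropout that is higher on ACTH, where the lean is systematic.

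Three stronger readings are tempting, and the documents do not support them.
- A reader might infer that the arms can never be equal. That holds for 45 completers or 45 randomised. If the trigger means the 45th enrolled patient, with earlier dropouts excluded, the evaluable set can be even and the arms equal. The plan does not define the set.
- A reader might infer that the plan contradicts itself outright. It does not: scale by scale on one responder metric, the two sentences are complements, and the parallel wording makes that a natural reading. The conflict needs the per-subject reading, or different metrics in the two sentences.
- A reader might infer that this rule alone decides whether the trial stops. Stage 1 is also a safety analysis, and the DSMB may meet at any time over safety. The rule governs only the Stage 1 efficacy halt.

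A further fair objection is that proportions do not settle everything. Suppose 25 per arm are randomised and 5 ACTH patients drop out. If dropouts count as non-responders, both denominators are 25 and the proportion rule equals the count rule, so the halt probability under the planned effect is 9%, not 3%. This stands, and it limits what the fix can promise.

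**Conclusion.** The concern holds in limited form. As worded, the rule compares numbers and can halt at identical response rates; that follows from arithmetic alone. The size depends on the split. Under the planned effect the halt probability ranges from about 1.5% to 9% between 23 v 22 and 20 v 25, against about 3% by completer proportion. With no effect it ranges from 11% to 46% between 25 v 20 and 20 v 25, against 29-34%. It is negligible at 22 v 23 and small on average with equal dropout. These probabilities rest on the assumed normal model, equal effects on both scales and a correlation of 0.6. The halt/continue overlap is real but depends on the reading. The point is worth correcting because the comparison is the plan's stated Stage 1 efficacy criterion and the remedy is nearly free. It does not show that an effective drug is likely to be halted.

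**What to change.** Keep the existing comparison but express it as the proportion of responders within each arm. State the denominator and the analysis set, including what the 45th subject refers to and how dropouts are handled, and use the same metric in both sentences. Reconcile the two sentences by stating whether the two-scale condition applies per scale or per subject, so that exactly one of halt or continue applies to any data set. Because a halt also ends study treatment, the choice of reading belongs to the sponsor and the DSMB; this point asks only that the sentences agree.

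The cost is a few sentences in the protocol and the DSMB instructions, with no added data. The downside is that the denominator is a choice. Completer proportions remove the arm-size dependence but ignore dropouts. Randomised patients with dropouts as non-responders keep the randomised comparison but count dropout against an arm, so they do not deliver the 3% figure when the imbalance comes from dropout. Whichever is chosen should be fixed before the look.

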Candidates must fulfill **all** of the following criteria before being included in the study:

1. Have documented diagnosis of Relapsing MS as defined by McDonald Criteria 2011 Revision for at least 6 months
2. Age range of 18 to 65 years old, inclusive at time of screening
3. Have been treated with interferon beta 1a or 1b, glatiramer acetate, fingolimod, dimethyl fumarate or teriflunomide for at least 6 months, with reported adherence rate of at least 75%, at time of screening
4. Have an EDSS score of 0 to 4, inclusive
5. Have MFIS ≥ 38 or FSS ≥ 36 , BDI-II ≤ 19 , and ESS ≤ 9
6. Women of childbearing potential must employ proven methods to prevent pregnancy during the course of the trial
7. Able to understand the purpose and risks of the study
8. Must be willing to sign an informed consent
9. Must be willing to follow the protocol requirements
10. Subject must agree not to receive any live or live-attenuated vaccine during the trial

Exclusion Criteria

Candidates will be excluded from study entry or participation if **any** of the following exclusion criteria exist at any time during the study:

1. Have any of the contraindications for Acthar Gel as listed in the approved label, including sensitivity to proteins of porcine origin.
2. Had treatment of systemic or oral corticosteroids of any type in 90 days prior to baseline/randomization
3. Had a relapse or documented objective neurologic worsening in 90 days prior to baseline/randomization
4. Has concurrent neurological disease other than multiple sclerosis
5.
 - a. Any history of sleep apnea
 - b. History (within the last 90 days) of nocturnal pain and/or nocturnal spasms that interferes with or interrupts sleep, or uncontrolled nocturnal restless leg syndrome
6. History of psychosis, bipolar disorder, mania/hypomania
7. History of coronary heart disease, congestive heart failure, chronic pulmonary disease, emphysema, anemia, bleeding disorder, gastrointestinal bleeding, intestinal ulcer, clinically significant cardiac arrhythmia, Type I or II diabetes, uncontrolled hypertension, seizure disorder, cardiac arrhythmia, immune deficiency disorder, HIV-AIDS, tuberculosis, or dysthyroidal state (patients with a history of hypothyroidism or hyperthyroidism, which has been corrected to physiological levels will not be excluded)
8. History of substance abuse, other than tobacco within the past 5 years or current alcohol dependence

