Data forms will be faxed to the data coordination center within 3 business days after each study visit and processed by staff trained in data entry procedures. The forms will be entered by two staff working independently. The completeness of the data and whether the data values are in an appropriate range will be checked periodically. Study sites will be asked to complete data clarification requests for confirmation of missing data or questionable information.

Statistical/Analytical Plan

Primary endpoint

Statistical analysis will be performed to test the change from baseline to end of study in two fatigue measures (MFIS and FSS) to be completed by patient at baseline, Week 8, Week 16, Week 24, and Week 28.

Secondary endpoint

Statistical analysis will be done to test the change from baseline to end of study in depression, sleepiness, and quality of life measures (BDI-II, ESS, and SF-36) to be completed by patient at baseline, Week 8, Week 16, Week 24, and Week 28.

All AEs are to be coded and grouped by organ system. AEs will also be tabulated by severity and by relationship and summarized by treatment group. Summary tables of the AEs will be presented to show the incidence and frequency by treatment group and by study site.

Statistical method

This study will collect longitudinal data that consists of repeated measures on each individual. The mixed-effects regression model for the analysis of longitudinal data will be used to test the changes of the fatigue scores over time.

Sample Size Justification

Ninety subjects will be recruited and randomized 1:1 to receive ACTH or placebo in a subject and examining physician-blinded manner. If the MFIS score decreases from 38 for about 20% with standard deviation =16.4 in the 45 patients who received ACTH, the power to reject the null hypothesis in a paired t-test with alpha=0.5 would be 86%. If the difference of the changes of MFIS score between two treatment group is 7.6 with within group standard deviation=16.4 in the 90 patients, the power to reject the null hypothesis in a t-test with alpha= 0.5 would be 87%. Ziemssen and colleagues (Ziemssen, Hoffman, Apfel, & Kern, 2008) studied the effect of glatiramer acetate on fatigue in MS patients. Glatiramer acetate was found to be associated with a reduction in absence from work and a significant reduction in fatigue symptoms, as measured by MFIS. The data from Ziemssen et al. were used for the sample size calculation for this study.

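### The Stage 1 halting rule counts 20% responders instead of using the MFIS and FSS scores, which makes it less sensitive to an ACTH arm that does worse than placebo

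*Combined protocol and SAP*

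**What the plan says.** Section C, Patient Monitoring and Evaluation, sets one look for safety and efficacy, made by the unblinded clinical and biostatistical members of the DSMB once the 45th patient has completed Week 16. Enrolment pauses meanwhile.

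- Halt condition: "If more subjects in the placebo arm demonstrate 20% or greater improvement than in the ACTH arm on both the MFIS and FSS".
- Continue condition: "If the ACTH arm is equal or superior to the placebo arm in MFIS and/or FSS, the study will continue".

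The halt condition compares numbers of patients who improve by at least 20%. The continue condition does not say whether it compares those counts or the scores. Neither has a margin or an error rate, and no reason is given for the 20% cut.

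Elsewhere the same scores are used in full. Under Statistical/Analytical Plan, Statistical method: "The mixed-effects regression model for the analysis of longitudinal data will be used to test the changes of the fatigue scores over time". The Sample Size Justification also works in mean scores: "If the difference of the changes of MFIS score between two treatment group is 7.6 with within group standard deviation=16.4 in the 90 patients". Inclusion Criteria, item 5, needs only one of the two fatigue scales to be high: "Have MFIS ≥ 38 or FSS ≥ 36 , BDI-II ≤ 19 , and ESS ≤ 9".

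**The concern.** Both scales are numeric. A responder cut treats an improvement just under 20%, no change and a marked worsening alike. Harm on ACTH shows only as a shortage of responders, and 22 patients per arm leave little information to spare. The cut is also relative to baseline. A patient admitted on FSS alone has an MFIS below 38, and so becomes an MFIS responder on less than 0.20 × 38 = 7.6 points.

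This is the only pre-specified efficacy halt. If it misses an inferior arm, the trial goes on to recruit another 45 patients. The halt is also decided on a different quantity from the one tested at the end.

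**Working it through.** **Inputs from the protocol.** Baseline MFIS is 38 and the change is about 20% (Sample Size Justification: "If the MFIS score decreases from 38 for about 20% with standard deviation =16.4 in the 45 patients who received ACTH"), so the responder cut is 7.6 points, the same size as the planned effect. The SD is 16.4. Allocation is 1:1, so 45 patients give about 22 per arm.

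**Assumptions not in the documents.** Changes are normal. FSS has the same standardised effect and cut as MFIS. The MFIS-FSS correlation of changes is 0.7 (range 0.5-0.9). Placebo mean change is 0. Data are complete, and simple means stand in for the mixed model.

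**The plan's own figures.** The Stage 1 rule has no stated error rate to reproduce. The 86% paired power does reproduce (n = 45, 7.6/16.4, two-sided alpha 0.05: 86.0%), which supports reading 16.4 as the SD of change and the printed alpha of 0.5 as a misprint. The 87% two-group power does not: 45 per arm gives 58%, and 87.1% needs 90 per arm. That is a separate matter. Only the effect and SD are used below.

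**Step 1: information on one scale.** The probability of response is P(Z > (7.6 − mean improvement)/16.4): 50.0% at a mean improvement of 7.6, 32.2% at 0 and 17.7% at −7.6.

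- Responder contrast at the planned effect: (0.500 − 0.322)/√[(0.500×0.500 + 0.322×0.678)/22] = 1.22.
- Mean contrast: 7.6/(16.4 × √(2/22)) = 7.6/4.94 = 1.54.
- Information kept by the cut: (1.223/1.537)² = 0.63.

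**Step 2: halting on one scale.** The exact binomial probability that placebo has more responders is 8.5% with the planned benefit, 43.6% with no effect and 82.9% with ACTH 7.6 points worse. Halting on the sign of the mean difference, Φ(−d/4.94), gives 6.2%, 50% and 93.8%. With no effect, tied counts occur 1 − 2 × 0.436 = 12.8% of the time and count as continue. On one scale they account for the whole no-effect gap.

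**Step 3: halting on both scales.** Simulation with 22 per arm and 60,000 trials per scenario. Entries are the probability of halting at correlation 0.7, with the range over 0.5-0.9 in brackets.

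| True state of ACTH | 20% responder rule | Mean change, zero cut | Mean change, 0.75-point margin |
|---|---|---|---|
| 7.6 better (planned) | 2.5% (2-4) | 2.5% (2-4) | about 2% |
| 3.8 better | 10% (8-13) | 13% (10-17) | 10% |
| 2 better | 17% | 23% | 18% |
| No effect | 27% (24-32) | 37% (33-43) | 31-32% |
| 3.8 worse | 51% (48-54) | 69% (66-72) | 63% |
| 7.6 worse | 73% (71-75) | 90% (89-92) | 87% |

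The zero cut happens to match the responder rule's wrong-halt risk at the planned benefit. Subtracting from 100% gives the misses: 27% against 10% at 7.6 worse, 49% against 31% at 3.8 worse, and 73% against 63% with no effect.

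**Step 4: other inputs, wrong-halt risk matched at the planned benefit.**

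- Correlation 0.3-0.8, placebo change 0-7.6 and baseline 38-60: an arm 7.6 worse is missed 22-33% against 9-11%; a useless arm, 71-78% against 60-68%.
- FSS effect half that of MFIS: the ratio of misses falls to 1.15 (no effect), 1.4 (3.8 worse) and 1.6 (7.6 worse).
- SD 12: ratios 1.27, 2.4 and 8. SD 20: ratios 1.13, 1.4 and 2.0.
- 18 per arm after 20% dropout (0.8 × 22 = 17.6): gaps of about 9-10, 16-18 and 17-20 points.
- If both scales must be met by the same patient: 14-23% against 2-4% missed at 7.6 worse, with a wrong-halt risk of 6-8%.

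The direction does not reverse in any of these.

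**The case against.** The documents set no target error rate that the rule fails. Being slow to halt on 45 patients is a defensible choice. The look is also a safety review by unblinded members, and the DSMB may meet whenever safety worries it (Members and Responsibilities of DSMB). All of that stands: the point is lost sensitivity, not a broken rule.

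Three stronger readings are tempting, and none is supported.

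- **The cut is why a useless arm passes.** It is not the main reason. The mean-change rule also misses a useless arm about 63% of the time, because placebo must be ahead on both scales and the bar is near zero. Ties matter too: letting them halt while keeping the 20% cut raises the no-effect halt rate from about 27% to 39-40%, above the mean-change rule's 37%, but doubles the wrong-halt risk from 2.5% to about 5%. Ties do not explain everything. Broken at random, with the wrong-halt risk re-matched at 3.9%, the halt rates are 33% against 44% (no effect), 57% against 75% (3.8 worse) and 78% against 93% (7.6 worse).
- **Worsening on ACTH is invisible to the rule.** A 7.6-point deficit lowers the response rate from 32% to 18%, and the rule then halts about 73% of the time.
- **Mean change carries no extra risk for an effective drug.** That holds only at the full planned benefit. With a zero cut, the halt rate is 13% against 10% at a true benefit of 3.8 points, and 23% against 17% at 2 points.

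The FSS inputs, the correlation and the placebo change are assumptions, and the size of the gain depends on them.

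**Conclusion.** The concern holds as a loss of sensitivity to an ACTH arm that does worse than placebo. In the base case the responder rule misses an arm 7.6 points worse nearly three times as often as a mean-change rule with the same wrong-halt risk at the planned benefit, and an arm 3.8 points worse about 1.6 times as often. For a useless arm the difference is modest, at about 10 percentage points. If the FSS effect is only half the MFIS effect, the first ratio falls to about 1.6.

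The advantage is not just a matter of matching at the most favourable point. With the halt rate matched at the 3.8-point benefit instead, the mean-change rule still halts 87% against 73% at 7.6 worse and 63% against 51% at 3.8 worse. The change is worth making. It does not call the final analysis into question.

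**What to change.** In Patient Monitoring and Evaluation, state the halt and the continue rule on one measure: the estimated ACTH-minus-placebo difference in mean change from baseline to Week 16, from the mixed model. Halt if it favours placebo on both MFIS and FSS; otherwise continue. Keep the 20% responder counts as a descriptive table for the DSMB.

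The Statistical method section names the model in one sentence, so it needs a treatment-by-visit term to define the Week 16 contrast.

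The sponsor should choose between a zero cut and a small margin in advance. A margin of about 0.75 MFIS points removes the rise in halting at a 3.8-point benefit, leaves 18% against 17% at 2 points, and keeps most of the gain for a worse arm. The simulation used the same standardised margin on FSS, 0.75/16.4 = 0.046 SD. The FSS SD is not in the documents and would have to be supplied.

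The cost is a short amendment before the DSMB sees unblinded Stage 1 data. The Week 16 scores are already collected, and the DSMB already includes a biostatistician. A mean difference is slightly less intuitive to clinicians than a responder count, which is why the table stays. What happens to participants after a halt is outside this point.
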